Semantic knowledge, or knowledge of a word's meaning, has strong ties to reading comprehension and long-term academic outcomes, particularly in the school years. Children with developmental language disorder (DLD), language impairment in the absence of any causal factors, often show deficits in semantic knowledge and acquisition. It is generally accepted that these deficits are driven by difficulty with the process of adding meaning to a new word with repeated exposures to the word, or configuration. What is unknown is what underlies deficits in configuration and whether these deficits vary across the DLD profile. The goal of this project is to elucidate the semantic learning deficits in DLD. Toward this goal, this project uses a combined electroencephalogram (EEG) - behavioral methods approach to examine the cognitive and linguistic processes engaged during semantic learning in school-age children with and without DLD. The inclusion of EEG will allow for a real-time examination of semantic learning and associated cognitive and linguistic processes. 10-12 year old children with and without DLD will complete a behavioral assessment battery and semantic learning task while their EEG is collected. Behavioral data will be analyzed for semantic learning group differences (Aim 1) and the types of errors that children make when they are unable to retrieve a correct meaning (Aim 2). EEG data will be analyzed in two ways. The event-related potential (ERP) analysis will examine changes in semantic processing, indexed by the N400, during learning (Aim 1). Time frequency analysis of the EEG will examine the engagement of neural processes associated with lexical retrieval (theta) and attention/inhibition (alpha) during learning (Aim 1). Behavioral and EEG methods will be combined to examine individual differences related to semantic learning outcomes and fine-grained differences in N400 learning effects across groups (Aim 2). Taken together, findings will inform our understanding of the nature of the semantic learning deficits in school-aged children with DLD. This understanding is prerequisite for targeted intervention that would help these children learn how to learn.

* Please provide a list of references to support the information found in the background and significance section.

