10-12 year old children, both those with typical language development and those with DLD, will serve as participants for this research. DLD is defined as impairment with language and no other deficit (e.g. neurological impairment, intellectual deficit, ADHD, autism, etc.) affecting language abilities.

* 4. Planned analyses:

Data analyzed will include behavioral performance on a semantic learning task (percent correct and analysis of incorrect responses) and EEG data time-locked to the novel word being learned. To compare behavioral semantic learning performance, behavioral data will be subjected to a one-way ANOVA to evaluate a possible effect of group (DLD, TL) on accuracy and the error analysis. To evaluate changes in brain processing of the novel word during

learning and potential group differences in neural processing. a 2 group (DLD, TL) x 3 presentation (1st sentence, 2nd sentence, 3rd sentence in the set) ANOVA will be run on the EEG data.

* 5. Potential benefits:

There are no direct benefits to the participants. Researchers will learn more about the nature of the semantic learning deficits in children with DLD.

* 6. Potential risks:

Participants will be exposed to very minimal risks. Due to the length of the assessments and semantic learning task, participants may experience some boredom and stress, which will not exceed the levels they experience in everyday life and breaks will be provided to alleviate any fatigue or boredom participants may experience. The EEG cap may be a little stressful for some participants and may seem itchy or uncomfortable. The risks and inconveniences associated with the assessments are reasonable in relation to the anticipated benefits discussed above.

* 7. Risk management procedures:

Participants will be informed about the procedure and the minimal risk. If at any time the participant does not feel comfortable with the EEG process, the experiment will be terminated. To help alleviate fatigue or boredom, breaks will be provided throughout the assessment session. To maintain confidentiality, a code number will replace participants' names on all of the information collected from them. All data will be marked with a participant code number only. Research records will be kept confidential to the extent allowed by law and stored in a locked filing cabinet at the Language Learning Lab and only personnel associated with this research will have access.

Research Design and Methods

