* Specify aims of the research that include the hypotheses to be tested, research questions to answer, data to be gathered and tested.

The central hypothesis of this research is that children with DLD engage cognitive and linguistic processes at different points during configuration compared to their typical peers, resulting in poorer semantic learning outcomes. Aim 1. To investigate the cognitive and linguistic processes underlying configuration in children with DLD and typical language (TL) peers. Aim 2. To investigate individual differences in configuration in children with DLD and TL peers. Toward these aims, we will administer a series of behavioral assessments to establish language status and a semantic learning task, during which we will collect EEG. See below for details.

* Use this space to provide a detailed list of every step you will take to test your hypothesis. Beginning with recruitment strategy, data collection , to analysis of research results.

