
PARTICIPANT INFORMATION

Study Population

Instructions: Enter the total number of adults and children you wish to recruit for your study. If you plan on recruiting members of a vulnerable population, indicate using the check boxes below and enter the total number expected for that category.

ADULTS (18+)

- Cognitively Impaired
- Prisoners
- Pregnant Women
- Other

Children

- Cognitively Impaired
- Prisoner/Detainee
- Pregnant Women

Other

* Population:
language impaired

TOTAL:

* Describe how the number of subjects was determined (e.g. statistical significance).

A priori power analyses were conducted with G*Power using preliminary data to determine sample sizes needed for the proposed project. For the behavioral data, the semantic learning accuracy analysis requires 16 participants/group for power=0.95, f=0.6, α =0.05, the error analysis requires 14 participants/group for power=0.95, f=0.6, α =0.05, and the regression requires 24 participants/group for power=0.95, f²=0.35 α =0.05. The ERP analysis requires 18 participants/group for power=0.95, f=0.6, α =0.05. The time frequency analysis requires 12 participants/group for power=0.95, f=0.6, α =0.05. This is consistent with evidence that time frequency analysis is more robust to noise than ERP requiring fewer trials and participants. Therefore, a targeted sample of 25 participants/group should easily provide at least power=0.8 for all proposed variables.

* List the criteria for inclusion and exclusion of subjects in this study.

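### Is the individual-differences regression underpowered within DLD, or only a repeat of the group difference?

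*Combined protocol and SAP*

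**What the plan says.** The sample-size paragraph under Participant Information gives a requirement for each analysis. For group accuracy, "the semantic learning accuracy analysis requires 16 participants/group for power=0.95, f=0.6, α =0.05". For the regression, "the regression requires 24 participants/group for power=0.95, f²=0.35 α =0.05". It concludes that "a targeted sample of 25 participants/group should easily provide at least power=0.8 for all proposed variables".

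The aims in Research Design and Methods include "Aim 2. To investigate individual differences in configuration in children with DLD and TL peers". The background section says "What is unknown is what underlies deficits in configuration and whether these deficits vary across the DLD profile", and later that "Behavioral and EEG methods will be combined to examine individual differences related to semantic learning outcomes".

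The Study Abstract's planned analyses say that "behavioral data will be subjected to a one-way ANOVA to evaluate a possible effect of group (DLD, TL) on accuracy and the error analysis", and add a group by presentation ANOVA for the EEG data. Research Design and Methods repeats both. Neither place mentions the regression. Nowhere does the document give its outcome, predictors, tested terms or treatment of group, or say whether it is pooled or fitted within each group.

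**The concern.** The regression has the largest requirement in the paragraph, so the target of 25 per group rests on it, and it is the only sized analysis that seems to serve the individual-differences part of Aim 2. Two features look troubling.

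First, its effect size (f²=0.35) almost equals the group effect assumed for accuracy (f=0.6, so f²=0.36). If group, or predictors standing in for group, supplied that effect, a significant result would restate the ANOVA while being read as evidence that learning varies with a child's profile. The risk is plausible: the CELF score defines the groups and is also part of the battery.

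Second, the background asks about variation across the DLD profile. A pooled regression does not isolate that. With two predictors in the 25 DLD children, power falls below 0.8, so a null result there would say little.

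The descriptions of the battery also differ. Research Design and Methods includes vocabulary measures that the table of measures lacks. The Flanker task appears only in the visit and measures tables. The nonword task is a recognition task in one table and a repetition task in the other.

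**Working it through.** **Inputs.** From the sample-size paragraph: f²=0.35, α=0.05, 24 per group (48 in total) for power 0.95, a target of 25 per group (50 in total), and f=0.6 for group accuracy. The number of tested terms is not given. Fixed predictors and no dropout are assumed.

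**Formula.** For u tested terms in a model with p predictors, power = P[F′(u, N−p−1; λ) > F(0.95; u, N−p−1)], where F′ is noncentral F and λ = N·f².

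**1. Reproducing the stated number.** With p = u, the total N for power 0.95 at f²=0.35 is:

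| Tested terms | 1 | 2 | 3 | 4 | 5 |
|---|---|---|---|---|---|
| Total N | 40 | 48 | 54 | 59 | 63 |

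Only two terms give 48: λ = 48 × 0.35 = 16.8, df 2 and 45, power 0.953. Two terms tested after group also need 48. A separate regression in each group of 24 (λ = 8.4) has power 0.791 for one term and 0.673 for two, so that reading does not reproduce the stated 0.95.

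**2. The promise of at least 0.8.** At N=50, λ = 17.5. Two terms give 0.961, whether tested alone or after group. The promise does not depend on the number being exactly two:

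| Tested terms, N=50 | 3 | 5 | 7 | 8 |
|---|---|---|---|---|
| Power | 0.935 | 0.878 | 0.817 | 0.786 |

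A pooled test keeps 0.8 up to seven terms.

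**3. Overlap with the group effect.** f=0.6 gives R² = 0.36/1.36 = 0.265; f²=0.35 gives R² = 0.35/1.35 = 0.259. Take accuracy as the outcome (an assumption), 25 per group, and no association within either group. Simulation of 40,000 studies gives:

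- Group plus one predictor, overall test: significant in about 96%. Noncentral F agrees: f²=0.36, two terms, N=50 gives 0.965. The predictor's own test stays at about 5%.
- Two predictors without group: 5% if they do not differ by group, and 34% at an assumed difference of 0.8 SD. If they track group fully, the limit is the same 0.965.
- Two predictors tested after group: 5%. Here f²=0.35 is a partial effect, and total R² = 1 − (1 − 0.265)/1.35 = 0.455.

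The stated N is compatible with all three.

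**4. A DLD-only model.** With n=25 and f²=0.35 carried into that group (an assumption), λ = 8.75:

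| Predictors | 1 | 2 | 3 |
|---|---|---|---|
| Power | 0.809 | 0.695 | 0.608 |

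Two predictors would need 31 children for 0.8 and 48 for 0.95.

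**The case for a change.** The strongest case for acting is that the analysis behind the sample size is not written down. One sample-size line covers both a sound test and one that mostly repeats the ANOVA, and the choice of predictors is left until data are in hand. A question about variation within DLD is better addressed by a DLD-only model or a group-by-predictor term. If the f²=0.35 association exists only in DLD, λ for the interaction is 0.35 × 25/2 = 4.375, and power is 0.54 for one term and 0.42 for two. Adding text would cost little.

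The specification gap stands. So does the caution that a pooled association should not be read as variation within DLD.

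The rest is conditional. Aim 2 covers both groups, so a pooled model is the natural reading; variation across the DLD profile is raised as background, not as a stated analysis. The closeness of 0.35 and 0.36 is weak evidence of overlap, because the same f=0.6 is entered for accuracy, errors, ERP and time-frequency alike. Even with group as a tested term, a misreading requires reporting the overall F without the predictor's coefficient. The sources of the regression cannot be said to disagree on its predictors, because none names any; a behavioral outcome with EEG predictors fits both descriptions. The battery differences are real but clerical, and they affect neither power nor the error rate.

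The back-calculation in step 1 also has limits. Accuracy and error analyses share f, power and α but are given 16 and 14 per group; as two-group ANOVAs these yield 0.907 and 0.863, so the paragraph's numbers are an imperfect guide to the tests behind them. At 25 per group that ANOVA has power 0.986, so the final promise is unaffected.

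**Conclusion.** No change follows. The plan's regression figure reproduces for a pooled two-term test (0.953 at N=48), and its promise of at least 0.8 holds for that test (0.961 at N=50) and for any pooled test of up to seven terms at f²=0.35. The 0.695 contradicts nothing stated, since it applies to a two-predictor model in DLD children alone, which is not proposed; with one predictor even that model reaches 0.809.

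Overlap with the group effect is possible but not shown. The chance of a significant overall result with no within-group association runs from 5% to 97% depending on choices the document leaves open. The ordinary choice, testing predictors after group, sits at 5% and needs the same 48 participants.

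What remains is missing detail about the model, which a competent analyst would supply by adjusting for group and reporting the predictors' own tests, together with clerical differences between the battery lists. No stated figure is wrong. The conclusion rests on a pooled model, fixed predictors, no dropout and the plan's own f²=0.35.

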Participant Recruitment: The PI has experience recruiting children with DLD and has established relationships with community agencies and professionals who work with these children, including local speech-language clinics, school districts, and literacy centers. Participants, both DLD and TL, will be recruited from these and other locations/professionals by way of flyers and in-person recruitment, when possible. General procedures: All participants will be screened over the phone or via email for language history, handedness, medication use and history of neurological disorders or dysfunction. Upon arriving at the lab, participants will complete a behavioral test battery including nonverbal cognition, receptive and expressive vocabulary, general language and verbal working memory measures. For the EEG task, an electrode cap, similar to a lycra swimcap, will be placed on the participant's head. The EEG caps used in the PI's lab are designed for research conducted with infants, children, adolescents, and adults. The EEG cap is being used as described for use with children according to the instructions for use document provided by the manufacturer. The researcher will apply a small amount of saline solution to each electrode (total: 64 on the scalp, another two above and below the left eye). The solution enables the small sponge in each electrode to expand and make contact with the scalp. When this contact is made, the measured impedance (measurement of resistance) decreases, and the impedance values can be observed on a computer monitor visible to the researcher. When the impedance level is decreased on most electrodes, the experiment can begin. Participants will be seated in an electrically-shielded room in the Language Learning Lab. The electrode cap will collect electrical activity from the brain as participants complete the semantic learning task, as described below. Participants will silently listen to naturally-paced sentences presented in sets of 3 sentences. The last word of each sentence will be a nonsense word. After each set of 3, the participant will be asked to provide the meaning of the nonsense word, if possible. An experimenter, sitting in the room but out of sight of the participant so as not to distract them, will write down the word provided by the participant. The participant will be asked to sit as still as possible while the stimuli are being presented, with the exception of when they are asked to define the nonsense word. Participants will be given breaks as needed. Following completion of the semantic learning task, participants will complete a word recognition task where they hear 200 nonsense words one at a time and push a button to indicate whether they've heard it before or not. Data analyzed will include behavioral performance on the semantic learning task (percent correct and incorrect responses for error analysis) and EEG data time-locked to the nonsense word in each sentence. To compare behavioral semantic learning performance and errors, behavioral data will be subjected to a one-way ANOVA to evaluate a possible effect of group (TL, DLD). To evaluate changes in brain processing of the novel word during learning and potential group differences in neural processing, a 2 group (TL, DLD) x 3 presentation (1st sentence, 2nd sentence, 3rd sentence in the set) ANOVA will be run on the EEG data.

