Participant exclusion criteria include: neurological disorders (i.e., ASD, ADHD), significant neurological history (i.e., head injury, epilepsy), left handedness, medication other than over-the-counter allergy medications, and/or nonverbal IQ less than 70, as measured by the Wechsler Intelligence Scale for Children. Performance on a standardized language omnibus assessment (Clinical Evaluation of Language Fundamentals-5 Core Language Scale; CELF) will be used to classify children as DLD if they earn a standard score of < 80, else they will be classified as TL. The use of a standard score of 80 on the CELF as a cut point for identification of DLD is supported by good sensitivity (0.97) and specificity (0.97). The use of this validated cut score is the best assurance that children will be correctly identified for their respective groups. DLD and TL groups will be equivalent on age, nonverbal cognition, handedness, and gender, as measured by parental responses to a questionnaire administered during participant intake.

If applicable, provide a rationale to support subject exclusion for populations who might benefit from participation in the research.

This age range was selected, in part, because the rate of vocabulary growth in children with DLD further decreases relative to TL peers around age 10.

Subject Recruitment

How will you contact potential subjects for recruitment?

- Record Review
- In-Person
- Classroom
- Flyer
- Third Party Referral
- Paid Advertisements
- Telephone
- Email
- Letter
- Electronic Participant Pool Recruitment
- Other

Please upload a copy of any recruitment language that will be used to introduce this study to potential participants.

Subject Screening

What instrument(s) will you use to determine subject eligibility?

- Survey/Screening/Checklist
- Phone Screen
- Health Records
- Other
- N/A

Survey/Screening/Checklist Detail

- Mail
- In-Person
- Online
- Other
- SONA

* Are you going to obtain informed consent prior to participant screening?

Yes No

* Explain how consent will be obtained prior to screening.

Consent will be obtained via phone or email, per parent request, following a script which has been uploaded.

Please upload instrument

Phone Screen Detail

* Are you going to obtain documentation of informed consent prior to participant screening?

Yes No

* Explain how documented consent will be obtained prior to screening?

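### The age range was chosen partly on a DLD growth argument, but the specified group tests have no age term; a prespecified age covariate would be a cheap, modest gain

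*Combined protocol and SAP*

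**What the plan says.** All references are to the combined protocol and SAP.

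- **Population.** The Study Abstract (Subjects) enrols "10-12 year old children, both those with typical language development and those with DLD". The rationale that follows the inclusion and exclusion criteria gives, as one part of the reason for this window, that "the rate of vocabulary growth in children with DLD further decreases relative to TL peers around age 10".
- **Behavioural tests.** Research Design and Methods says that "behavioral data will be subjected to a one-way ANOVA to evaluate a possible effect of group (TL, DLD"). This covers both accuracy and the error analysis.
- **EEG test.** The same section specifies "a 2 group (TL, DLD) x 3 presentation (1st sentence, 2nd sentence, 3rd sentence in the set) ANOVA". The Planned analyses item of the Study Abstract describes the same two models.
- **Age in the design.** The inclusion and exclusion criteria say that "DLD and TL groups will be equivalent on age, nonverbal cognition, handedness, and gender", with a parental intake questionnaire as the source. This is a balance statement, not a model term.
- **Individual differences.** Aim 2 is "To investigate individual differences in configuration in children with DLD and TL peers". The sample size section powers a regression (24 per group, f²=0.35) but no section names its predictors.
- **Sample size.** For accuracy, "the semantic learning accuracy analysis requires 16 participants/group for power=0.95, f=0.6, α =0.05". The target is 25 per group, said to give power of at least 0.8 throughout.

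**The concern.** The plan uses a change in language growth at about age 10 as one reason for its age window, then specifies group tests in which age plays no part. Balance on age protects the comparison from confounding by mean age. It does not remove the spread of outcomes that arises because, within each group, some children have just turned 10 and others are close to the upper limit. If accuracy or the EEG measures vary with age in this range, that spread goes into the error term although age is already obtained. The stated tests also give no view of whether the group difference varies with age.

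At stake are some precision and a piece of description relevant to Aim 2. The validity of the group comparison is not at stake. Settling the covariate beforehand also avoids a later choice between adjusted and unadjusted results.

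**Working it through.** **Inputs from the documents:** f=0.6, α=0.05, 25 per group (N=50), ages 10-12.

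**Assumptions (not in the documents):** within-group correlation r between age and outcome of 0.2, 0.3 or 0.4; a smaller effect f=0.4 as a sensitivity case; age spread uniformly over the window for the interaction.

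**1. The plan's own figure.** For a two-group one-way ANOVA the noncentrality is λ = f²N, with 1 and N−2 degrees of freedom. At f=0.6 and N=50, λ = 0.36 × 50 = 18 with 48 error df, and power is 0.986. The claim of at least 0.8 at 25 per group is therefore met for this test. (Separately, 16 per group gives 0.907 by this F test, which needs 20 per group for 0.95. The figure of 16 reproduces only with a one-sided test. This does not affect the present point.)

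**2. Adding age to the behavioural models.** With groups balanced on age, the residual variance is multiplied by 1−r², so the standard error is multiplied by √(1−r²). The noncentrality becomes λ = f²N/(1−r²), with 47 error df.

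| r | Error variance removed (r²) | Fall in SE, 1−√(1−r²) | λ, f=0.6 | Power, f=0.6 | λ, f=0.4 | Power, f=0.4 |
|---|---|---|---|---|---|---|
| no age term | – | – | 18.00 | 0.986 | 8.00 | 0.791 |
| 0.2 | 4% | 2.0% | 18.75 | 0.989 | 8.33 | 0.807 |
| 0.3 | 9% | 4.6% | 19.78 | 0.992 | 8.79 | 0.827 |
| 0.4 | 16% | 8.3% | 21.43 | 0.995 | 9.52 | 0.856 |

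If age is unrelated to outcome (r=0), the lost degree of freedom leaves power at 0.986 (f=0.6) and 0.791 (f=0.4), unchanged to three decimals.

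**3. The EEG model.** In the 2 x 3 ANOVA, the group main effect is tested against between-child error. Presentation and group x presentation, which carry the change during learning, are tested against within-child error. Age is constant within a child, so an age main effect reduces only the between-child error. To remove age-related variation in change across the three sentences, the model also needs age x presentation. That term uses 2 df, taking the within-child error df from (50−2) × 2 = 96 to (50−3) × 2 = 94. The table above therefore does not carry over to the presentation effects.

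**4. Group x age.** Let the gap change by D within-group SDs across a window of W years. With uniform age, SD(age) = W/√12, and the difference of two slopes has noncentrality (D/W) × (W/√12) × √(25/2) = 1.02 × D. W cancels. With 46 df and a two-sided 0.05 test:

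- D=0.6: noncentrality 0.61, power about 9%
- D=1.2: noncentrality 1.22, power about 22%
- 80% power needs D of about 2.8

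**The case against.** The case against is substantial, and most of it stands as a limit on the point.

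- **A valid test already exists.** With groups equivalent on age, the unadjusted comparison estimates the average difference over the enrolled ages without confounding by mean age, which is what Aim 1 needs. A reader might infer that omitting age biases the result; the documents do not support that.
- **The rationale does not commit the plan to modelling age.** It is given as one reason among others, and it concerns vocabulary growth. A reader might infer that the plan expects the learning-task and EEG gap to widen between 10 and 12 and that pooling hides this. The documents nowhere say that these outcomes diverge with age, so that step is conjecture.
- **Age may enter elsewhere.** A reader might infer that no analysis uses age. A regression is powered and its predictors are not named, so the documents show neither that age is in it nor that it is left out. Only the specified group ANOVAs can be said to lack it.
- **The power gain is negligible at the plan's own effect size.** At f=0.6 it is at most 0.9 percentage points. It becomes visible only if the true effect is smaller.

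What remains is narrow. Balance on mean age does not take within-group age variance out of the error, and using a covariate that is already obtained costs almost nothing.

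**Conclusion.** The point holds as an optional improvement, not as an error. The specified group tests contain no age term although the age window was chosen partly on a growth argument, and any age-related variance within groups is left in the error. The benefit is a fall of about 2% to 8% in the standard error of the behavioural group difference if r lies between 0.2 and 0.4. That is worth little power at f=0.6 (0.986 to 0.989-0.995) and somewhat more at f=0.4 (0.79 to 0.81-0.86). Both r and f=0.4 are assumptions.

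The sample size is not called into question. Nor could 25 per group settle whether the gap changes with age: a widening of 1.2 SD across the window, as large as the whole group difference implied by f=0.6 (d = 2 × 0.6 = 1.2), would be detected only about 22% of the time. A non-significant group x age term would therefore not be evidence of a constant gap.

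**What to change.** In both the Planned analyses item of the Study Abstract and the analysis text of Research Design and Methods:

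1. Replace the group-only ANOVA for accuracy and errors with a model on group plus age at testing, centred at the sample mean.
2. In the 2 x 3 EEG model, add centred age and age x presentation. Age alone would sharpen only the between-group main effect.
3. Report group x age as a labelled exploratory estimate with a confidence interval, and state that power at 25 per group is about 9% for a 0.6 SD widening and 22% for 1.2 SD.
4. Name the predictors of the regression and say whether age is among them.

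**Cost.** One error degree of freedom in each behavioural model and one more where group x age is fitted. In the EEG model, one between-child df for age and two within-child df for age x presentation. No added participants, visits or measures. Age at testing can be derived from intake data; the documents do not state its unit, so the plan should say that it is recorded in months rather than whole years.
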